1. OBJECTIVES

The overall objective is to conduct a randomized, placebo-controlled, double-blind trial of PROSTVAC® in patients with clinically localized prostate cancer undergoing active surveillance to determine the immunologic response to PROSTVAC® and the clinical indicators of disease progression.

1.1 Primary Objectives

- 1.1.1 To determine the effect of PROSTVAC® on the change (from pre to post-intervention) in CD8⁺ positive cells in the stroma adjacent to tumor and within the malignant portion of the prostate biopsies.
- 1.1.2 To determine the effect of PROSTVAC® on the change in CD4⁺ positive cells in the stroma adjacent to tumor and within the malignant portion of the prostate biopsies.

1.2 Secondary Objectives (prioritized list)

- 1.2.1 To assess the effect of PROSTVAC® on PD-L1 positive cells in the stroma adjacent to tumor and within the malignant portion of the prostate biopsies.
- 1.2.2 To assess the correlation between the change in CD8⁺ and the change in PSA.
- 1.2.3 To assess the effect of PROSTVAC® on CD8⁺, CD4⁺, and PD-L1 positive cells in the benign portion of the prostate biopsies.
- 1.2.4 To assess the effect of PROSTVAC® on the change in PSA.
- 1.2.5 To assess the effect of PROSTVAC® on tumor grade (Gleason score).
- 1.2.6 To assess the effect of PROSTVAC on tumor extent (percent of positive random biopsy cores).
- 1.2.7 To compare the proportion of men on the two study arms with no cancer on post-intervention biopsy.
- 1.2.8 To assess the effect of PROSTVAC on the size of the dominant lesion on MRI (largest histopathologically confirmed lesion) in the subgroup of patients with MRIs pre and post-intervention.
- 1.2.9 To assess the effect of PROSTVAC® on circulating 15-Mer PSA-specific, MUC-1 and Brachyury-specific T cells.
- 1.2.10 To assess the effect of PROSTVAC® on soluble antibodies to tumor-associated antigens.
- 1.2.11 To assess the immunologic effects of PROSTVAC® in prostate tissue using multiplex immunofluorescence.
- 1.2.12 To assess the safety and feasibility of PROSTVAC® in the active surveillance population.
- 1.2.13 To assess the effect of PROSTVAC® on lower urinary tract symptoms (LUTS) in the active surveillance population.

2. BACKGROUND

2.1 Prostate Cancer

Due to widespread screening with the prostate-specific antigen (PSA) assay, prostate cancer is the most frequently diagnosed non-cutaneous cancer among U.S. men. While prostate cancer mortality has declined during the screening era, this has occurred at the cost of substantial over diagnosis and overtreatment, unnecessarily exposing many patients to side effects of therapy, such as erectile dysfunction, urinary incontinence, and proctitis [1, 2].

Population studies suggest that a substantial proportion of men diagnosed with localized prostate cancer in the US are over-treated [3-5]. This public health problem—unnecessarily aggressive treatment of tens of thousands of men each year who subsequently suffer chronic side effects—challenges us to develop innovative therapeutic models to refine treatment paradigms within this patient population.

In recent years, active surveillance has increasingly garnered attention as an alternative, and less morbid, approach to surgery or radiation in men with clinically localized, low-risk prostate cancer. Follow-up

assessments in patients on active surveillance include serial PSA measures, repeat prostate biopsy and, increasingly, prostate MRI. Most men on active surveillance followed for up to 15 years will not require treatment. However, up to one-third of active surveillance patients will undergo treatment within 2 to 5 years of initiating surveillance [6].

Development of intervention strategies to prevent disease progression in patients on active surveillance thus represents an important area of prostate cancer chemoprevention. Prior studies have yielded promising early results. The Prostate Cancer Lifestyle Trial compared intensive dietary and lifestyle modifications for men on active surveillance to usual care and reported a significantly lower rate of secondary treatment for the intervention arm after 2 years of follow-up [7]. The Reduction by Dutasteride of Clinical Progression Events in Expectant Management (REDEEM) trial assessed the efficacy of dutasteride in preventing disease progression in active surveillance patients. After 3 years, 38% and 48% of the dutasteride and control participants, respectively, had progressed by pathologic or therapeutic criteria, a relative risk reduction of 21% for dutasteride [8]. An ongoing multicenter study is evaluating whether a dietary intervention could delay disease progression in men on active surveillance [9].

However, definitive interventions for preventing clinical progression in active surveillance patients are lacking.

2.2 PROSTVAC®

An alternative and novel approach for delaying disease progression in men on active surveillance is immunotherapy. Prostate cancer presents an attractive model for immunotherapy based on several characteristics. It is a relatively slow-growing tumor, thus allowing time for elicitation of effective immune response. In addition, prostate cells express many tissue-specific proteins that could act as therapeutic targets. In the past decade, a variety of vaccines against prostate cancer have been developed and tested in clinical trials in metastatic castration-resistance prostate cancer patients [10]. Sipuleucel-T became the first prostate cancer vaccine approved by the FDA based on results of two randomized placebo controlled Phase III clinical trials that demonstrated an overall survival advantage with the use of Sipuleucel-T [11, 12]. Sipuleucel-T is a cell-based vaccine that employs the patient's own antigen-presenting cells that have been treated (*ex vivo*) with a recombinant fusion protein. Due to the complex preparation processes, the clinical adaption of this vaccine in the long-term prevention setting is likely to be limited.

Another therapeutic vaccine that has recently reported an overall survival advantage in prostate cancer is PSA-TRICOM (PROSTVAC®). PROSTVAC® is a poxviral vaccine using a vaccinia vector for priming and fowlpox vector for boosting. It contains PSA and three T-cell co-stimulatory molecules (B7.1, ICAM-1, and LFA-3). PROSTVAC® can be manufactured in large quantities, stored frozen for many years, and then thawed and injected into patients. Based on the RFP summary provided by the NCI, DCP, PROSTVAC® has been evaluated in 13 completed clinical trials with six additional trials in progress.

A Phase I study determined the safety and feasibility of PROSTVAC® in men with locally recurrent or progressive prostate cancer. PROSTVAC® was administered with initial subcutaneous injection of recombinant vaccinia (rV)-PSA-TRICOM and intraprostatic booster vaccinations with recombinant fowlpox (rF)-PSA-TRICOM. There were no dose-limiting toxicities. Common adverse events were fever and subcutaneous injection site reactions. The study also showed improved serum PSA kinetics and increased tumor infiltrates of CD4⁺ and CD8⁺ cells [13].

A double-blind, randomized, placebo controlled Phase II multicenter trial evaluated PROSTVAC® in 125 patients with minimally symptomatic castration-resistant metastatic prostate cancer. The priming and boosting vaccinations were given subcutaneously. PROSTVAC® was found to be well tolerated. Common adverse events included injection site reactions and fatigue. Although the progression free survival was similar between the two groups, PROSTVAC®-treated patients had an overall survival advantage. At 3

years post study, PROSTVAC®-treated patients had a 44% reduction in the death rate and an 8.5 months improvement in median overall survival compared to the placebo [14]. A smaller study evaluated PROSTVAC® in 32 patients with metastatic castration-resistant prostate cancer and reported an overall survival of 26.6 months with a median improvement in survival of 9.2 months compared with a Halabi-predicted survival (HPS) [15].

The consistent survival advantage observed in these studies has led to the design and initiation of a Phase III trial of PROSTVAC® in 1200 subjects with asymptomatic or minimally symptomatic castration-resistant prostate cancer.

In addition, evaluation of emerging data supports the use of immunotherapy earlier in the disease course and in patients with less aggressive disease and lower tumor burden [16, 17]. In one of the PROSTVAC® studies described above [15], patients with more aggressive or more advanced disease (HPS < 18 months) had a 2.3- month improvement over predicted overall survival, whereas those with less advanced or less aggressive disease (HPS ≥ 18 months) had an improvement in overall survival of 16.5 months or more. This supports the evaluation of PROSTVAC® in the active surveillance setting.

2.3 Rationale

In recent years, active surveillance has increasingly garnered acceptance as an alternative, and less morbid, approach to surgery or radiation in men with favorable-risk prostate cancer. However, definitive interventions for preventing clinical progression in active surveillance patients are lacking. Available data suggest that PROSTVAC® improved the overall survival in patients with castration-resistant prostate cancer and the survival benefit increased with less advanced or less aggressive disease. We, therefore, hypothesize that PROSTVAC® will prevent or delay disease progression in patients on active surveillance. We propose to conduct a randomized, placebo-controlled, double-blind trial of PROSTVAC® in patients with clinically localized prostate cancer undergoing active surveillance to assess the immunologic response to PROSTVAC® and its effect on clinical indicators of disease progression.

3. SUMMARY OF STUDY PLAN

This is a Phase II randomized, placebo-controlled, double-blind trial of PROSTVAC® in patients with clinically localized prostate cancer undergoing active surveillance. We plan to recruit men with a diagnosis of localized prostate cancer who are being monitored by active surveillance. Detailed inclusion and exclusion criteria are listed in sections 4.1 and 4.2.

Participants will undergo a screening evaluation in which the informed consent form and medical records and tissue release form will be signed in order to obtain information from urologic assessment, biopsy pathology reports, PSA test results, and biopsy tissues. Participants will undergo a brief physical exam and be evaluated for concomitant medications, medical history and baseline symptoms and signs. International Prostate Symptom Score (IPSS) will be obtained. Blood will be collected for complete blood count with differentiation (CBC-diff), comprehensive metabolic panel (CMP), and PSA. Screening visit procedures, including PSA, performed within 90 days prior to the Baseline Visit (first vaccine injection), may be applied toward eligibility.

Participants will also undergo a digital rectal exam (DRE) to confirm clinical stage at screening, if a DRE has not been performed within 180 days before the Baseline Visit.

Following the screening evaluation, eligible participants will be randomized 2:1 to receive PROSTVAC® or placebo. Randomization will be stratified according to the study site and the number of repeat biopsies following diagnosis (≤ 2, or >2). We plan to randomize 150 eligible men (i.e., 100 receiving PROSTVAC® and 50 receiving placebo).

Following randomization, participants will return for the Baseline Visit and be evaluated for weight, vital signs, AEs and concomitant medications. Blood will be collected for isolation of peripheral blood mononuclear cells (PBMC). Blood will also be collected for PSA and for serum soluble antibodies to tumor-specific antigens. Blood will be collected prior to administration of the vaccine injection. Participants will receive a priming vaccination with subcutaneous injection of PROSTVAC-V or placebo, injected into the upper outer thigh or upper arm. Participants will be provided with instructions for caring for injection site. Participants will be instructed to record adverse events and concomitant medications throughout the intervention. Participants will be reminded to avoid close contact or household contact with the following high-risk individuals for three weeks after the Day 1 vaccination or until the vaccination site heals completely: (a) children ≤ 3 years of age, (b) pregnant or nursing women, (c) individuals with prior or concurrent extensive eczema or other eczematoid skin disorders, (d) individuals with other acute, chronic, or exfoliative skin condition, or (e) immunocompromised or immunosuppressed persons (by disease or therapy).

On Day 14, 28, 56, 84, 112, 140 following the baseline visit, participants will return for booster vaccinations with subcutaneous injection of PROSTVAC-F or placebo injected into the upper outer thigh or upper arm. It is recommended to alternate the injection sites. Other evaluations at each visit include weight, vital signs, AEs and concomitant medications. At the Day 84 visit International Prostate Symptom Score will be obtained, blood will be collected for PSA and for CBC-diff and CMP. CMP and CBC test results will be evaluated prior to administering the scheduled vaccine to determine whether the injection should be given or omitted. If needed, the labs can be done on a different day prior to the day of the scheduled vaccine injection, but the labs and the vaccine injection should fall within the window specified on the schedule of events.

Participants will return for the post-intervention visit 7-14 days after the last scheduled dose of vaccine. Blood will be collected prior to the biopsy procedure for CBC-diff, CMP, PSA, PBMCs, and serum. Participants will be evaluated for weight, vital signs, AEs and concomitant medications. International Prostate Symptom Score will be obtained. DRE will be performed at the discretion of the individual urologist. TRUS-guided prostate biopsy or targeted prostate biopsy using MR-US fusion will be performed as part of the routine care of patients on active surveillance. The results of all PSA tests performed during the intervention will be collected. Pre- and post-intervention biopsy pathology reports will be collected and submitted to the University of Arizona Early Phase Chemoprevention Consortium Office. Unstained slides from the pre- and post-intervention prostate biopsies will be requested from the institutional pathology lab for analysis of the change in immune infiltrates in the target tissue.

If available, reports from the prostate MRI scans performed (and companion pathology reports) from 3 years prior to and 6 months after the study intervention will be collected and submitted to the University of Arizona Early Phase Chemoprevention Consortium Office to capture the lesion size information.

Study subjects will be followed for 30 days after the last study dose is given. Participants will continue to record adverse events during the follow-up period. The diary will be mailed back to the study staff in a pre-addressed, stamped envelope. Study staff will contact the subject by phone, if necessary, to clarify any of the diary entries.

Participants will return for a follow-up visit 6 months after the post-intervention biopsy or 6 months after the last study dose is given, if no post-intervention biopsy was performed, as part of the standard-of-care. Blood will be collected for PSA. International Prostate Symptom Score, interval medical history, and documentation on whether participant is still on active surveillance will be obtained. DRE will be performed at the discretion of the individual urologist. Patients who have undergone prostatectomy, radiation therapy or focal prostate cancer therapy are exempt from the six-month follow-up visit requirement.

4. PARTICIPANT SELECTION

4.1 Inclusion Criteria

- 4.1.1 Biopsy-proven (consisting of ≥ 10 tissue cores) adenocarcinoma of the prostate with cancer present in at least one biopsy core, either random or targeted, in the most recent biopsy.
- 4.1.2 All prior biopsies must meet the following: $\leq 50\%$ of the total number of random biopsy cores positive for cancer
 - Gleason score $\leq (3+4)$
- 4.1.3 Clinical stage $\leq T2a$ by DRE
- 4.1.4 Biopsies performed at outside institutions should have Gleason score confirmed at the study site by a GU pathologist to ensure eligibility.
- 4.1.5 Pre-intervention biopsy tissue (most proximal to enrollment) containing sufficient tumor tissue to cut 5-10 unstained slides confirmed to be available upon request.
- 4.1.6 Screening serum PSA < 20 ng/mL. For men treated with 5-alpha-reductase inhibitors (e.g., finasteride, dutasteride), PSA needs to be < 10 ng/mL.
- 4.1.7 Hematological eligibility parameters:
Neutrophil count $\geq 1,200/\text{mm}^3$ (≥ 1.2 k/ μL)
Stable platelet count $\geq 75,000/\text{mm}^3$ (≥ 75 k/ μL)
- 4.1.8 Hepatic and renal function eligibility parameters:
Bilirubin ≤ 1.5 mg/dL (or ≤ 3.0 mg/dL for patients with Gilbert's syndrome)
ALT and AST ≤ 2.5 x ULN
Serum creatinine ≤ 1.5 x ULN
- 4.1.9 Karnofsky $\geq 70\%$; see Appendix A.
- 4.1.10 Must agree to use medically acceptable barrier and/or chemical method of contraception while on study and for at least one month following the last vaccine injection because the effects of PROSTVAC® on the developing human fetus at the recommended therapeutic dose are unknown. Should a participant's partner become pregnant or suspect she is pregnant while the participant is participating in this study, the study physician should be informed immediately. In the event a participant's partner becomes pregnant, the study sponsor may request additional information regarding the course of the pregnancy and if the pregnancy is carried to term, the birth of the child (i.e., the outcome of the pregnancy).
- 4.1.11 Ability to understand and the willingness to sign a written informed consent document.
- 4.1.12 No planned prostate biopsies during the intervention until after the post-intervention biopsy.
- 4.1.13 Men on stable doses of 5-alpha reductase inhibitors are eligible as long as there is no planned dose change while on study.

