8.2 Secondary Endpoints

- 8.2.1 To assess the effect of PROSTVAC® on the change in PD-L1 positive cells in the stroma adjacent to tumor and within the malignant portion of the prostate biopsies. The change will be compared between participants treated with PROSTVAC® and those treated with placebo. A subgroup analysis will be performed to compare the change in PD-L1 positive cells between study groups in specimens collected by targeted biopsy.
- 8.2.2 To assess the correlation between the change in CD8⁺ and the change in PSA. The correlation between the change in CD8⁺ in the stroma adjacent to tumor and within the malignant portion of the prostate biopsies and the change in PSA (from baseline to 6 months (5-7 months) post-intervention) in participants treated with PROSTVAC® will be examined.
- 8.2.3 To assess the effect of PROSTVAC® on the change in CD8⁺, CD4⁺, and PD-L1 positive cells in the benign portion of the prostate biopsies. The change will be compared between participants treated with PROSTVAC® and those treated with placebo.
- 8.2.4 To assess the effect of PROSTVAC® on the change in PSA. The change in PSA from baseline to 6 months (5-7 months) post-intervention will be compared between participants treated with PROSTVAC® and those treated with placebo.
- 8.2.5 To assess the effect of PROSTVAC® on tumor grade progression, defined as a post-intervention

- Gleason score of $\geq 4+3$ using all biopsy data, i.e., from random and target biopsy cores. Proportion of men with post-intervention Gleason score of $\geq 4+3$ will be compared between the treatment groups. In addition, this endpoint will be evaluated in the subgroup of patients in whom MRI-targeted biopsies were obtained pre- and post-intervention.
- 8.2.6 To assess the effect of PROSTVAC on tumor extent based on the percent of positive random biopsy cores. The change in tumor extent will be compared between the treatment groups.
 - 8.2.7 To assess the proportion of men with no cancer in the post-intervention biopsy between participants treated with PROSTVAC® and those treated with placebo. This analysis will utilize all biopsy data, i.e., from random and target biopsy cores.
 - 8.2.8 To assess the effect of PROSTVAC on the size of the dominant lesion on MRI (largest histopathologically confirmed lesion) in the subgroup of patients with MRIs pre and post-intervention.

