13.5 Secondary Objectives, Endpoints, Analysis Plans

The secondary objectives are to determine the effects of PROSTVAC® on the change in PD-L1 positive cells in the stroma adjacent to tumor and within the malignant portion of the prostate biopsies, the correlation between the change in CD8⁺ and the change in PSA, to determine the effect of PROSTVAC® on the change in CD8⁺, CD4⁺, and PD-L1 positive cells in the benign portion of the prostate biopsies, to determine the effect of PROSTVAC® on the change in PSA, to assess the effect of PROSTVAC® on tumor grade and tumor extent, to assess the proportion of men with no cancer on the post-intervention biopsy, to assess the safety and feasibility of PROSTVAC®, and to assess the effects of PROSTVAC® on LUTS.

The secondary endpoints include the change in PD-L1 positive cells in the stroma adjacent to tumor and within the malignant portion of the prostate biopsies, the correlation between the change in CD8⁺ and the

change in PSA, the change in CD8⁺, CD4⁺, and PD-L1 positive cells in the benign portion of the prostate biopsies, the change in PSA, the tumor grade progression, the change in tumor extent, safety and feasibility, and the change in International Prostate Symptom Score. In addition, a comparison will be made between the two study arms on the proportion of patients with no cancer on the post-intervention biopsy. Similarly, MI techniques will be performed, as necessary. A two-sided two-sample t test at a significance level of 5% will be performed to compare each of the secondary endpoints between the PROSTVAC® and placebo groups. Pearson correlation coefficient will be derived to evaluate the correlation between the change in CD8⁺ and the change in PSA for participants treated with PROSTVAC®. Fisher's exact test will be performed to compare the proportion of patients with no cancer on the post-intervention biopsy and the proportion of men with an increase in Gleason score to $\geq 4+3$ between the two groups. These secondary analyses are considered exploratory, therefore, no correction will be performed for multiple comparisons.

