For both primary and secondary endpoints, data will be tested for non-normality and outliers. If the normality assumption is violated, a potential transformation will be sought. If no suitable transformations can be found, nonparametric tests (e.g. Wilcoxon Rank Sum test and Spearman correlation coefficient) will be used. If outliers are detected, sensitivity analysis will be performed to evaluate the impact of the outliers on the effects of PROSTVAC®. In addition, we anticipate observing a missing rate of 25% or greater for both primary and secondary endpoints. The missing rates for both PROSTVAC® and placebo groups will be reported and compared. Also, regression models will be performed to identify the potential variables that are predictive of the missing endpoints or probabilities.

Descriptive statistics of the type and frequency of all adverse events will be generated, including 95% confidence intervals. For each type of the adverse events, a Fisher's exact test will be performed to compare the frequency of the adverse event between the two groups.

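### Tumor extent is tested as an unadjusted change in the percent of positive random cores; adjusting for entry extent gives a more precise comparison at no cost

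*Combined protocol and SAP*

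**What the plan says.** - **Entry.** Section 4.1.1 asks for a biopsy of at least 10 cores, with "cancer present in at least one biopsy core, either random or targeted, in the most recent biopsy". It does not say how many must be random. Section 4.1.2 limits the share "of the total number of random biopsy cores positive for cancer" to 50% and sets no lower limit.
- **Endpoint.** Section 8.2.6 is "To assess the effect of PROSTVAC on tumor extent based on the percent of positive random biopsy cores", and "The change in tumor extent will be compared between the treatment groups". Objective 1.2.6 uses the same measure. By contrast, 8.2.5 (grade) and 8.2.7 (no cancer) use random and targeted cores together.
- **Analysis.** Section 13.5: "A two-sided two-sample t test at a significance level of 5% will be performed to compare each of the secondary endpoints". No covariate is named. If the data are not normal, "If the normality assumption is violated, a potential transformation will be sought", and then a rank test is used. Of the secondary analyses as a whole it says: "These secondary analyses are considered exploratory".
- **Post-intervention biopsy.** Sections 3 and 7.4 allow either a TRUS-guided biopsy or a targeted MR-US fusion biopsy. Neither says that random cores must be taken.
- **Not stated.** The documents give no power, effect size or SD for tumor extent, no expected share of men who enter on a targeted core alone, and no rule for a biopsy without random cores.

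**The concern.** A change score subtracts the entry value in full, including its sampling error. Here the entry value is a proportion on perhaps a dozen cores, and eligibility depends partly on that same count. Two drifts follow, neither caused by treatment. Men who entered with random hits were partly selected on a chance high count and tend to fall at the next biopsy. Men who entered on a targeted core alone, with random cores taken and all negative, have entry extent 0%; their change can only be zero or positive.

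Randomization spreads both drifts evenly over the arms in expectation, so they do not bias the arm difference. They do add variance, and a t test on change leaves that variance in. The transformation and rank-test fallback deals with shape, and neither step brings entry extent into the comparison. Tumor extent is one of the few direct clinical indicators of progression in the trial, so a real effect is somewhat more likely than necessary to be reported as no difference.

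**Working it through.** **The plan's own figure.** There is none for tumor extent. The only stated power is for the primary endpoints. With 100 × 0.9 × 0.7 = 63 and 50 × 0.9 × 0.7 = 31.5 (stated as 31), SD ratio 2:1, d = 0.63 and two-sided alpha 0.025, a Welch calculation gives 89.4% against the stated 90%. This point does not affect it.

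**Men available for extent.** A biopsy without tumor is a valid 0%, so only the 10% attrition in 13.4 applies: 100 × 0.9 = 90 and 50 × 0.9 = 45.

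**Why adjustment helps.** Let X be entry extent, Y post-intervention extent and b the within-arm slope of Y on X. Then

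Var(Y − X) = Var(Y − bX) + (1 − b)² Var(X).

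The change score fixes the slope at 1. With few cores and selected entry, b is below 1 and the last term is pure loss.

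**Size, by simulation.** All of these inputs are assumptions: 12 random cores at each biopsy; per-core positivity Beta(1,5), (1,8), (2,10) or (0.7,5); 20% or 48% of men with a positive targeted core; entry rules 4.1.1 and 4.1.2 applied. The comparison is a Welch t test on change against a linear model of post-intervention percent on arm and entry percent with HC2 standard errors, 3000 trials per setting.

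*No vaccine effect.* Men positive on a targeted core only are 5-27% of entrants. Their mean change is +4 to +8 points, against −1.4 to −2.9 in the others. Type I error is 4-6% for both methods.

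*40% cut in per-core positivity:*

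| Positivity | Targeted core positive | t test on change | Adjusted | Gain (points) |
|---|---|---|---|---|
| Beta(1,5) | 20% | 0.83 | 0.90 | 7 |
| Beta(1,5) | 48% | 0.80 | 0.88 | 8 |
| Beta(1,8) | 20% | 0.67 | 0.78 | 11 |
| Beta(1,8) | 48% | 0.60 | 0.73 | 13 |
| Beta(2,10) | 20% | 0.79 | 0.90 | 11 |
| Beta(2,10) | 48% | 0.76 | 0.89 | 13 |
| Beta(0.7,5) | 20% | 0.72 | 0.81 | 9 |
| Beta(0.7,5) | 48% | 0.66 | 0.75 | 9 |

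Over repeat runs the gain is about 6-14 points.

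*Prevention* (placebo positivity grows by 7 points per core, vaccine blocks it): power is 69-79% on change and 73-86% adjusted. Over repeat runs the gain is about 3-9 points. Across all scenarios the variance of the arm difference falls by about 6-27%.

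**How much is due to the entry rule?** The 40% cut was repeated with at least one positive random core required at entry, which removes every targeted-only man. Example pairs are 0.86/0.91, 0.72/0.83, 0.83/0.91 and 0.80/0.86, gains of 5, 11, 8 and 6 points; over repeat runs the gain is about 5-12. The variance cut is 11-21%, against 15-27% with those men included. Most of the gain is therefore ordinary baseline adjustment.

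**Do random-negative men dilute the effect?** In a separate calculation their share f was set by hand (Beta(2,8), 12 cores, 90 v 45). Power of the t test on change:

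| Effect | f = 0 | 10% | 20% | 30% |
|---|---|---|---|---|
| 40% cut in all men | 90% | 86% | 82% | 77% |
| 40% cut, none in random-negative men | 90% | 81% | 70% | 58% |
| 9 points of growth prevented in all men | 87% | 88% | 89% | 89% |

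In the first two rows adjusted power also falls, from 96% to 92% and from 96% to 78%. Adjustment is better at each f, but the dilution remains. (This set used model-based standard errors and imposed shares, so its gains of 15 and 20 points at f = 30% are not the ones relied on.)

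**The case against.** The strongest reply is that this is generic. Baseline adjustment would help most change scores in 13.5, the endpoint is exploratory, no power is claimed for it, and the t test is valid. All of that stands and limits the severity. It does not remove the gain, which appears in every setting tried and under both types of effect.

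A reader might go further and infer that admitting men on a targeted core alone is what costs the endpoint its power, or that the trial cannot see benefit in these men. The documents do not support either reading:

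- The hypothesis in 2.3 is that the vaccine prevents or delays progression. A man at 0% can show that as a smaller rise than on placebo, and in that case power does not fall as the share of such men grows.
- A loss from dilution needs an effect that shrinks existing disease. Its size cannot be computed, because the documents do not give the share of these men.
- Sections 8.2.5 and 8.2.7 use all cores, and 8.2.8 follows the dominant MRI lesion where scans exist. Only one of several measures has the floor.
- Starting at 0% presumes that random cores were taken. If none were, entry extent is undefined.

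It is also fair to say that the simulated model had only arm and entry percent as covariates; the stratification factors were not simulated.

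**Conclusion.** The point holds as one of efficiency. The planned comparison of tumor extent is valid but less precise than one adjusted for entry extent: about 6-27% of the variance of the arm difference is avoidable. That is worth roughly 6-14 power points for a 40% cut in per-core positivity and 3-9 points for a prevention effect, with type I error near 5%. These ranges rest on assumed core counts, positivity distributions, targeted-core rates and effect sizes, so they indicate scale and are not predictions for this trial.

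The entry rule in 4.1.1 adds to the noise but is not the main source of the loss, and adjustment does not lift the floor at 0%. The plan also lacks a rule for men with no random cores at entry or post-intervention. Severity is low: the endpoint is secondary and exploratory, and the primary analysis is unaffected.

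**What to change.** In 8.2.6 and 13.5:

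1. Make the outcome the post-intervention percent of positive random cores. Compare arms by linear regression with robust standard errors, with entry percent of positive random cores and the stratification factors (study site, number of repeat biopsies) as covariates. Report the adjusted arm difference in percentage points with its confidence interval.
2. Set entry extent to 0 only when random cores were taken and all were negative. Treat extent as missing, not 0, when no random cores were taken at entry or post-intervention, and apply the missing-data approach of 13.1.
3. Report raw change by arm, split by whether all random cores were negative at entry, as description only, with the number of such men in each arm.

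The cost is SAP wording. Sections 3 and 7.4 already have the pre- and post-intervention pathology reports collected. No extra patients, biopsies or visits are needed.
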